5.5 Prior and Concomitant Therapy

Prior and concomitant therapies include following the current weight management protocol which promotes diet and lifestyle changes to aid in weight reduction. Subjects' prior failed trial or coached programs for weight loss will be recorded in their medical records.

The multidisciplinary team consisting of a pediatric endocrinologist or pediatric gastroenterologist, and a dietitian at the weight management clinic, will evaluate the patient at baseline, at 3 and 6 months after the insertion of the balloon, and at 9 and 12 months, which would be after the removal of the balloon. The dietitian at the weight management clinic will review the PN Q and the food record template and guide the diet modification accordingly. Subjects will have follow up psychology visits to support adherence and address any emotional

and social adjustment concerns. Blood and urine samples will also be collected at months 3, 6, 9, and 12, after the IGB insertion. The subjects and their parents will be contacted by phone by a GI nurse to answer telephone questionnaire in between the visits on site at 4 days, 2 weeks, and at months 1, 2, 4, 5, 7, 8, 10, and 11, after the IGB insertion. Details of the diet and lifestyle regimen before and after the balloon insertion will be documented in the subject's medical records.

Before the balloon insertion, the number of calories recommended will be individualized based on the subject's age, gender, and level of physical activity, with a goal of achieving weight loss of 0.5 lb. per week. After the balloon insertion, the number of calories recommended will depend on the subject's current intake and weight trajectory. With regards to physical activity, subjects will be encouraged to engage in at least a total of 60 minutes of moderate to vigorous intensity physical activity on a daily basis.

For subjects with type 2 diabetes, the pediatric endocrinologist ([name]) will be managing treatment for this co-morbidity while on the study. All medications that subjects are using during the study will be recorded at the start of the study and updated throughout the study on a medication reconciliation sheet. Subjects will be instructed to do self-monitoring of blood glucose, and the dose of medications for diabetes will be modified by pediatric endocrinology in order to prevent hypoglycemia or prevent worsening of diabetes. HgA1c will be measured every 3 months, and subjects will be reassessed for their diabetic condition every three months.

5.6 Packaging and Labeling

Upon receipt of the IGB devices from Apollo Endosurgery, assurance of the investigational device label will be affixed by the study coordinator to the packaging of each device. See below:

“CAUTION – Investigational Device. Limited by Federal (or United States) law to investigational use”

5.7 Masking/Blinding of Study

Not applicable

5.8 Receiving, Storage, Distribution and Return

5.8.1 Receipt of Investigational Devices

The Orbera IGB devices will be shipped to the study coordinator from Apollo Endosurgery in Austin, Texas. Upon receipt of the devices, the study coordinator will perform an inventory and fill out a device accountability log to ensure that all devices are accounted for. Any discrepancies, damaged, or unusable devices in a given shipment will be documented in the study files and the company will be notified. The devices will then be taken by the study coordinator to where they will be stored in the study coordinator's locked office space.

5.8.2 Storage

The Orbera IGB will be stored with the rest of the supplies that will be stored in the study coordinator's locked office space which is a secure location with limited access to prevent unintended or unauthorized use of the device.

5.8.3 Distribution of Study Device

The Orbera IGB will be distributed according to the clinical protocol of how clinical intragastric balloons are distributed. The serial number on the Orbera IGB will be matched up to a subject's medical record number. This de-identified data will then be recorded on the device accountability log using subject number instead of medical record number.

5.8.4 Return or Destruction of Study Device

At routine intervals and at the completion of the study, there will be a reconciliation of devices shipped, devices utilized, and devices remaining. This reconciliation will be logged on the Device Accountability form, signed and dated. Any discrepancies noted will be documented, the sponsor-investigator will be notified and an investigation will be conducted to determine the cause of the discrepancy. Devices destroyed on site will be documented in the study files.

6 Study Procedures

6.1 Insertion of Balloon by PI or Co-PI

If the subject still meets all the inclusion and exclusion criteria after the baseline evaluations and the pregnancy test are completed, s/he will undergo physical examination followed by placement of the IGB by a gastroenterologist ([name] or [name]) via endoscopic approach under monitored and controlled anesthesia. Esophagogastroduodenoscopy (EGD) is very safe and routine diagnostic approach for adolescents with gastrointestinal disorders.[25]

- All subjects with type 2 diabetes will be on metformin or insulin prior to the balloon placement. The metformin would be discontinued 48 hours before the balloon placement and resumed after discharge from the hospital once oral intake has normalized. The metformin or insulin will be continued as needed and will be weaned only as tolerated based on blood glucose values and/or HgA1C, as determined by pediatric endocrinology.
- Subjects will be observed and undergo monitoring of their blood glucose values, and these children will be evaluated and closely followed by pediatric endocrinology in the perioperative period. All subjects will undergo a preanesthetic medical examination by a pediatric endocrinologist.
- Blood glucose values in these subjects would be measured prior to the procedure and subsequently every 4 hours during and for 48 hours after the procedure. Insulin

doses will be adjusted if there is an increase in blood glucose after dexamethasone administration. Insulin doses would also be adjusted by pediatric endocrinology in those subjects who are not able to tolerate oral intake or have hypoglycemia/hyperglycemia.

- Metformin, the only oral hypoglycemia approved for treatment of type 2 diabetes in children, would be discontinued prior to balloon placement in subjects on metformin monotherapy due to the risk of lactic acidosis. Blood glucose values would be monitored in the perioperative period. Subjects would receive insulin in the perioperative period in the event of hyperglycemia. Subjects on insulin, subjects who were on metformin prior to balloon placement, and subjects with any symptoms of hypoglycemia will be asked to monitor blood glucose in the post-operative period by performing self-monitoring of capillary blood glucose a minimum of 5 times daily (before each meal, at bedtime, and at 3 a.m.). Hyperglycemia will be managed by pediatric endocrinology. Metformin would be restarted after oral intake has normalized.
- All subjects will have a diabetes action plan in the medical records, at school, and at home that will clearly outline treatment for hypoglycemia.
- The balloon will be removed immediately if pediatric endocrinologist feels that medical management of hypo/hyperglycemia is challenging and/or has deteriorated by symptoms resulting from the insertion of the IGB.

6.3 Indications for Follow-up Endoscopy

After the balloon is inserted, an endoscopy will be required if:

- persistent abdominal pain
- GERD symptoms
- evidence of GI bleeding
- evidence of new microcytic anemia
- balloon deflation on abdominal ultrasound or x-ray

6.4 Indications for Removal of IGB

The balloon will be retrieved at the time of the endoscopy if the subject has any of the following:

- Esophagitis - Los Angeles grade C or D
- gastric or duodenal ulcers with high risk stigmata (visible vessel or sign of recent bleeding such as clots in the stomach) or deep ulcer that is more than 10 mm wide and 5 mm deep, worrisome for impeding perforation (see section below - Ulcers)
- balloon wedged in the antrum with clinical symptoms of gastric outlet obstruction or balloon partially/completely deflated

- new acute pancreatitis diagnosed by cross sectional imaging or serum lipase more than 3 times the upper normal limit for the institution (see section below - Pancreatitis)

Ulcers:

An ulcer will be defined as ≥ 5 mm in diameter with unequivocal depth by endoscopy. The ulcer is endoscopically significant if it is ≥ 3 cm in length and ≥ 1 cm in width. Effort will be made to capture clear images with an accessory of known dimensions next to the lesion to estimate size.

- If an ulcer is ≥ 2 cm in diameter or width (the smaller measurement between the length and width), or if there are any stigmata of increased risk of bleeding, such as visible vessels, clots, etc., the device will be removed.
- If an ulcer is smaller than 2 cm in diameter but endoscopically significant, signs of healing defined by a 25% reduction in either length or width should be observed after the first 8 weeks of medical therapy and a 50% reduction from baseline in either length or width after an additional 8 weeks of medication. If an endoscopically significant ulcer does not show signs of healing after 8 weeks of medication, shows less than 50% reduction in length or width after 16 weeks of medication, the device will be removed.
- Blood hemoglobin will be monitored during scheduled or unscheduled endoscopies in subjects who have ulcers or report signs of upper GI bleeding (hematemesis or melena).
- Subjects in whom an ulcer is diagnosed and treated will have endoscopic confirmation of complete resolution.

Pancreatitis:

New onset abdominal pain (developed after acute accommodative balloon symptoms of balloon placement has resolved) suggestive of pancreatitis (epigastric / right upper quadrant in location with or without radiation to the back, persistent (>3 hours in duration), and associated with nausea, vomiting, or new poor oral tolerance justify checking amylase and lipase levels.

- If pancreas enzymes are $> 3X$ upper limit of normal for institution,
 - In a systemically ill patient with evidence of severe acute pancreatitis (requiring > 3 days hospitalization, OR evidence of end organ damage [acute renal failure, respiratory distress, or meeting SIRS (systemic inflammatory response syndrome) criteria for sepsis], OR cross sectional imaging suggestive of severe acute pancreatitis [evidence of pancreas necrosis or new pseudocyst], the balloon will be removed and close clinical follow-up of these severely ill patients will be required.
 - In a patient who does not meet the criteria of severe pancreatitis, pancreas enzymes will be repeated in 48 hours with clinical follow-up.
- If pancreas enzymes are $< 3X$ upper limit of normal for institution,
 - In a systemically ill patient with evidence of severe acute pancreatitis (requiring > 3 days hospitalization, OR evidence of end organ damage [acute

renal failure, respiratory distress, or meeting SIRS (systemic inflammatory response syndrome) criteria for sepsis], OR cross sectional imaging suggestive of severe acute pancreatitis [evidence of pancreas necrosis or new pseudocyst], the balloon will be removed and close clinical follow-up of these severely ill patients will be required.

- If typical pain persists for > 48-72 hours, pancreas enzymes will be repeated in 48 hours with clinical follow-up.
- If pain resolves within 48-72 hours, clinical follow-up will be required.

In addition to the above mentioned endoscopic findings, the balloon would be removed in case of:

- severe anticipated or unanticipated adverse events
- pregnancy
- subject and family request for balloon removal
- risk of continuation of the trial, in the opinion of the PI, due to psychosocial circumstances, noncompliance with the required follow-ups and removal, or if the subject is moving and there is a risk of not being able to remove the balloon at 6 months.

Otherwise, the balloon will stay in place and the subject will be treated symptomatically, as described in Section 6.2.

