3.4 Primary Safety Endpoints

- Incidence of all serious adverse events including unanticipated adverse effects (balloon migration, small bowel obstruction, luminal GI perforation, ulcer formation, liver abscess formation, bleeding, biliary obstruction or injury, aspiration, infection, abdominal pain requiring hospitalization, nausea and dehydration requiring intravenous fluids, and death). All adverse events will be captured and graded for severity using Common Terminology Criteria for Adverse Events (CTCAE) scale. [27]
- Early balloon intolerance requiring removal.
- Balloon deflation rates (see Orbera PMA)

4 Subject Selection, Enrollment and Withdrawal

Adolescents age 14-17 who are seen at Mayo Clinic-Rochester in community pediatrics, pediatric GI, pediatric endocrinology, or the pediatric weight management clinic, or at Mayo Clinic Health System (MCHS) with a $BMI > 35 \text{ kg/m}^2$ with one severe comorbidity or $BMI > 40 \text{ kg/m}^2$ with two or more mild comorbidities as per the ESPAGHAN guidelines for

bariatric intervention in children with severe obesity. [14] Recent meta-analysis supported the safety and benefit of IGB use in higher BMI (range 35-55).[24] Subjects that meet these criteria can be referred to the PI, co-investigators, or study coordinator to approach for possible participation in this research study.

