6.5 Indications for Repeat Endoscopy after Removal of IGB

At the time of balloon removal, a repeat endoscopy will be indicated if the following conditions were found:

- Esophagitis - Los Angeles grade C or D
- Significant gastric ulceration (ulcers are bigger than 10 mm with high risk stigmata such as visible vessel, adherent clot, or clean base with > 5 mm depth)

If the gastric ulcers persist despite the proton pump inhibitor increase, then other etiologies will be excluded (Crohn's disease, celiac disease or hypergastrinemia) by performing mucosal biopsies from the ulcer and further blood work.

Subjects with any device related adverse events (AE) or gastric ulcerations at the time of device removal will continue on medical proton pump inhibitors therapy with dose and duration of therapy determined by the study PI. These subjects will be followed clinically until complete resolution. Repeat endoscopy to assess for resolution will be done at the discretion of the study PI depending on the severity of endoscopic finding at the time of removal and the clinical need based on best clinical guidelines and practices.

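### Section 6.4 gives two answers on removing the balloon for a deep ulcer 1 to 2 cm wide, and Sections 6.4, 6.5 and 1.5.2 differ on how healing of an ulcer found at removal is confirmed

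*Combined protocol and SAP*

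**What the plan says.** **Removal, opening list of Section 6.4.** The list begins "The balloon will be retrieved at the time of the endoscopy if the subject has any of the following". One entry is a "deep ulcer that is more than 10 mm wide and 5 mm deep, worrisome for impeding perforation (see section below - Ulcers").

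**Removal, Ulcers paragraph of Section 6.4.** It gives no depth threshold for removal. The device comes out for bleeding stigmata or on size: "If an ulcer is ≥ 2 cm in diameter or width (the smaller measurement between the length and width"). It also defines a further class: "The ulcer is endoscopically significant if it is ≥ 3 cm in length and ≥ 1 cm in width". For that class below the size trigger, it says "If an ulcer is smaller than 2 cm in diameter but endoscopically significant, signs of healing defined by a 25% reduction in either length or" the other dimension is expected after 8 weeks of treatment, and a 50% reduction after 8 more. The device is removed if either target is missed.

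**Confirming healing.** Section 6.4: "Subjects in whom an ulcer is diagnosed and treated will have endoscopic confirmation of complete resolution". Section 6.5 first says that repeat endoscopy is indicated for ulcers over 10 mm that have high-risk stigmata or a clean base more than 5 mm deep. For subjects with ulceration at removal it then says "Repeat endoscopy to assess for resolution will be done at the discretion of the study PI", according to severity and clinical need. Section 1.5.2, on ulcers seen at the 6-month removal, provides for acid suppression and clinical follow-up until resolution and does not mention endoscopy.

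**Role in the trial.** Section 3.4 includes ulcers in the primary safety endpoint: "luminal GI perforation, ulcer formation, liver abscess formation, bleeding". Section 7 sets the sample at 12 subjects and calls the results largely descriptive.

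**The concern.** Safety is part of the primary objective, the subjects are 14 to 17 years old, and the protocol itself ties the deep ulcer to a worry about perforation. If the text supports both immediate retrieval and a course of treatment with the balloon in place, handling of that lesion depends on the paragraph the endoscopist has in mind.

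The second disagreement concerns ascertainment. Table 2 schedules endoscopy only at insertion and removal, and Section 6.3 adds others only for pain, reflux symptoms, bleeding, new anemia or deflation. An ulcer that causes none of these would be seen first at removal, which is where the three sections part ways. Resolution could then be established by endoscopy in some subjects and clinically in others, with no stated reason for the difference.

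**Working it through.** No power or sample-size calculation bears on this point. The check applies each text as written to the same lesions.

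**1. Inputs (Section 6.4, ulcers without stigmata).** L is length and W is width, with W the smaller dimension; D is depth.
- Opening list: retrieve if W > 1 cm and D > 5 mm.
- Ulcers paragraph: remove if W ≥ 2 cm. If W < 2 cm, L ≥ 3 cm and W ≥ 1 cm, treat and judge healing at 8 weeks and at 8 + 8 = 16 weeks, which reproduces the plan's 16-week figure.

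Two readings are assumed. The 5 mm figure is taken as more than 5 mm. Diameter in the healing rule is taken as the smaller dimension, as the preceding bullet defines it. If it meant the longest dimension, no ulcer could be both under 2 cm and at least 3 cm long, and the healing rule would apply to nothing.

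**2. Results.**

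| Ulcer (L × W, depth) | Opening list | Ulcers paragraph |
|---|---|---|
| 3.5 × 1.5 cm, 6 mm | retrieve now | healing checks at 8 and 16 weeks |
| 2.5 × 1.5 cm, 6 mm | retrieve now | no removal trigger, no healing schedule |
| 2.5 × 2.5 cm, 6 mm | retrieve now | remove |
| 2.5 × 2.5 cm, 3 mm | no trigger | remove |
| 3.5 × 1.5 cm, 3 mm | no trigger | healing checks at 8 and 16 weeks |

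Only the first row is a head-on conflict. Its region is L ≥ 3 cm, 1 cm < W < 2 cm, D > 5 mm, no stigmata. At W ≥ 2 cm a deep ulcer is removed under both texts.

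**3. Confirmation of healing.** Take a clean-based ulcer 12 mm across and 3 mm deep, found at removal and treated. It meets the 5 mm minimum diameter in Section 6.4's definition.
- Section 6.4: healing must be confirmed by endoscopy.
- Section 6.5: outside the indicated group, because there are no stigmata and the base is not deeper than 5 mm; repeat endoscopy is discretionary.
- Section 1.5.2: clinical follow-up only.

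The same holds for any ulcer found or still present at removal and treated, if it falls outside Section 6.5's indicated group. Inside that group, Sections 6.4 and 6.5 both point to endoscopy.

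**4. Scale.** One subject in 12 is 1/12 = 8.3 percentage points of any proportion with the device removed or with resolution confirmed endoscopically.

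**The case against.** The best defense is that Section 6.4 is cumulative. The list says that any one finding leads to retrieval, the Ulcers paragraph adds further grounds, and the balloon stays only when nothing in the section has triggered removal. On that reading the 3.5 × 1.5 cm, 6 mm deep ulcer is retrieved, and the healing checks serve ulcers not already caught. The Ulcers paragraph also never says outright that the device is kept; that follows from its healing schedule.

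This reading is possible, but the protocol states no order of precedence, and the list sends the reader to the Ulcers paragraph for this very lesion. The pancreatitis text in the same section also tells against it. There the list retrieves the balloon at lipase more than 3 times the upper limit, while the detailed paragraph repeats the enzymes in 48 hours if the case is not severe. The detailed paragraphs therefore do not simply add to the list. What stands is that investigators could diverge, not that they will.

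On healing, one can say that Section 6.5 is the specific rule for findings at removal and overrides Section 6.4. That too is unstated, and the Section 6.4 sentence has no such limit. Section 6.5's indicated group does narrow the overlap.

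Two further inferences are tempting but unsupported:
- **That the 16-week schedule clashes with a 6-month implant.** In about 26 weeks it can finish only for ulcers found by about week 26 − 16 = 10. But the checks decide early removal. Sections 3.1 and 6.7 take the balloon out at 6 months regardless, which ends that question, and Section 6.5 covers ulcers present then. The schedule is cut short, not contradicted.
- **That the size classes are defective because a 2.9 × 1.9 cm shallow ulcer escapes the healing checks while a 3.0 × 1.0 cm ulcer does not.** Any definition with two minimum dimensions can do this. It is a preference about classes, not a contradiction.

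**Conclusion.** The point holds within limits. Section 6.4 gives conflicting directions for ulcers without stigmata that are at least 3 cm long, above 1 and below 2 cm wide, and more than 5 mm deep. Sections 6.4, 6.5 and 1.5.2 conflict on confirming resolution for treated ulcers found or persisting at removal, outside Section 6.5's indicated group.

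A reader might infer that the primary safety result depends on the paragraph used. It does not: Section 3.4 counts incidence, and an ulcer counts as ulcer formation whether the balloon is kept or removed. Nor does either reading alter the stopping rules in Section 8.5, although perforation is listed there. What depends on the reading is whether the device is removed, how long the subject is exposed to it, and how resolution is ascertained.

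The size-and-depth window is narrow, and the readable text gives no ulcer rate, so how many of the 12 subjects might fall in it is unknown. The finding rests on the two readings stated in the check and on the absence of a precedence rule. It should be fixed, because the correction is cheap and the lesion is one the protocol singles out, but it does not undermine the trial's design.

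**What to change.** Reconcile the opening list and the Ulcers paragraph of Section 6.4, so that one set of criteria, or an explicit order of precedence, decides removal. If depth is meant to count, say so in both places; if not, remove the cross-reference that implies it. Make Sections 6.4, 6.5 and 1.5.2 agree on how resolution is confirmed for ulcers found or still present at removal, and record the method used for each ulcer so that the safety report can describe it. Which clinical criteria are kept is for the sponsor to decide.

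The cost is amendment wording in three sections, with no added subjects. Depending on the sponsor's choice on confirming healing, a few repeat endoscopies may follow; in adolescents that burden should be weighed in making the choice.

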6.5 Indications for Repeat Endoscopy after Removal of IGB

At the time of balloon removal, a repeat endoscopy will be indicated if the following conditions were found:

- Esophagitis - Los Angeles grade C or D
- Significant gastric ulceration (ulcers are bigger than 10 mm with high risk stigmata such as visible vessel, adherent clot, or clean base with > 5 mm depth)

If the gastric ulcers persist despite the proton pump inhibitor increase, then other etiologies will be excluded (Crohn's disease, celiac disease or hypergastrinemia) by performing mucosal biopsies from the ulcer and further blood work.

Subjects with any device related adverse events (AE) or gastric ulcerations at the time of device removal will continue on medical proton pump inhibitors therapy with dose and duration of therapy determined by the study PI. These subjects will be followed clinically until complete resolution. Repeat endoscopy to assess for resolution will be done at the discretion of the study PI depending on the severity of endoscopic finding at the time of removal and the clinical need based on best clinical guidelines and practices.

